4.7.3. Pain Upon Motion (PUM) Scale

The change from baseline in the PUM scale for the affected shoulder at the Day 64 and Day 95 Visits will analyzed.

25-April-2022

4.7.4. Patient-reported Global Severity of Adhesive Capsulitis Scale

The change from baseline in the Patient-reported Global Severity of Adhesive Capsulitis Scale at the Day 22, 43, 64 and 95 Visits will be analyzed.

4.7.5. Patient-reported Change in Severity of Adhesive Capsulitis Scale

The rating (response) in the Patient-reported Change in Severity of Adhesive Capsulitis Scale at the Day 22, 43, 64, and 95 Visits will be analyzed.

4.7.6. Investigator Assessment of Improvement with Treatment

Investigator assessment of improvement with treatment at the Day 64 and Day 95 Visits will be analyzed.

A responder is defined as a response of "Very Much Improved", "Much Improved" or "Minimally Improved" in the investigator assessment of improvement with treatment.

4.7.7. Subject Satisfaction with Treatment

Subject satisfaction with treatment at the Day 64 and Day 95 Visits will be analyzed separately for individual questions of subject satisfaction prior to receiving treatment and subject satisfaction compared to better shoulder.

A responder is defined as a subject with a response of "Very Satisfied", "Satisfied" or "Somewhat Satisfied" in the subject satisfaction with treatment.

4.8. Safety Parameters

4.8.1. Adverse Events

Adverse event verbatim terms as reported by the investigator will be mapped to system organ class (SOC) and preferred term (PT) using the Medical Dictionary for Regulatory Activities (MedDRA) dictionary. The dictionary version to be used will be defined in the DMP.

4.8.1.1. Treatment Emergent Adverse Events (TEAEs)

TEAEs are defined as any AEs that occur or worsen (increase in severity) on the same day or after the treatment initiation.

The following rules will apply in cases where the start date of an AE is known:

- If the AE onset date is prior to first administration of the study drug, then the AE will not be considered a TEAE.
- If the AE onset date or date of AE worsening is equal to or later than first administration of the study drug, then the AE will be considered a TEAE.

Refer to section 6.3.2.1 to identify TEAE status when start date of an AE is unknown.

25-April-2022

4.8.1.2. Intensity of Adverse Events

Intensity (or severity) of AEs will be graded as "Mild", "Moderate" or "Severe". For AEs with missing severity, the most severe assessment will be imputed for analyses as "Severe", following worst case principle.

4.8.1.3. Relationship to Study Drug

Causal relationship of AEs to study drug will be classified by the Investigator and will be reported as follows:

- Not related.
- Unlikely related.
- Possibly related.
- Probably related.

Related adverse events are AEs with the relationship described by the investigator as "Probably related" or "Possibly related". "Not related" or "Unlikely related" causality assessments are considered as negative causality.

Any AE with a missing relationship to study drug will be considered as related to study drug for the analyses, following worst case principle.

4.8.1.4. Adverse Event Categorization by Treatment Session

- The AEs will be associated with the treatment session based on the start date of the AE compared to injection date, as below:
- Treatment session 1: First injection date until start of second injection.
- Treatment session 2: Second injection date until start of third injection.
- Treatment session 3: Third injection date until start of Day 64 Visit.

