3.4. Dose Interruption

All eligible subjects will receive their first dose of study treatment on Day 1. At each subsequent treatment visit (the Day 22 and 43 Visits) each subject will be evaluated to determine if they can continue treatment.

Subjects that have all 5 measurements of AROM and PROM (forward flexion, internal rotation, external rotation, abduction, and shoulder extension) of the affected shoulder that are > 90% of the baseline contralateral shoulder ROM and have an adapted ASES function subscale score of > 40 in the affected shoulder should not be dosed unless the investigator believes that the clinical benefit outweighs the risk.

Subjects who are not treated at the Day 22 Visit will continue in the study and will be reassessed at the Day 43 Visit and may be treated based on these assessments and investigator discretion. Subjects who are not treated at the Day 22 and/or Day 43 Visits will complete all other activities required for those visits and are also expected to complete the Day 64 and Day 95 Visits.

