3.16.1. Adverse Events

All adverse events (AEs) will be recorded from the time informed consent is signed through the Day 95/ET Visit, or for 28 days after the last dose of study treatment for those who early terminate.

Conditions existing prior to screening will be recorded as part of subject's medical history.

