- Study drug related TEAEs by treatment session
- Duration (1-7 days, 8-14 days, 15-21 days, > 21 days) of study drug related TEAEs.
- Serious TEAEs.

- TEAE of special interest.
- TEAE of special interest by severity.

Most common non-serious TEAEs by order of frequency (Most frequent, 2nd most frequent, and 3rd most frequent) will be summarized by PT. Most common non-serious AEs are those that at least 5% of the subjects reported at least once (using PT).

The following listings will be presented by subject:

- All AEs.
- AEs resulting in death.
- Non-fatal serious AEs.
- AEs resulting in drug interruption/withdrawal.
- AEs resulting in study discontinuation.

Refer to Table 16 for computation of duration of AEs.

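### The session windows for adverse events depend on how many injections a subject received, and events after Day 64 in fully dosed subjects belong to no session

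*SAP*

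**What the plan says.** SAP 4.8.1.4 assigns each adverse event to a session by comparing its start date with the injection dates, in three lines:

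- Session 1 opens with injection 1 and closes when injection 2 is given.
- The line for session 2 has the same form: "Treatment session 2: Second injection date until start of third injection"
- The line for session 3 differs, because it closes at a visit and not at an injection: "Treatment session 3: Third injection date until start of Day 64 Visit"

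There is no fourth category, and no fallback end for a session whose next injection does not take place.

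The rule feeds one display named in SAP 7.10.2, "Study drug related TEAEs by treatment session", tabulated by system organ class and preferred term.

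Three other provisions bear on it:

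- **Collection period (SAP 3.16.1).** "All adverse events (AEs) will be recorded from the time informed consent is signed through the Day 95/ET Visit". A separate limit applies to early terminators, whose events are collected up to 28 days from their final injection.
- **TEAE status (SAP 4.8.1.1).** Any event starting or worsening on or after first dosing qualifies, with no upper time limit.
- **Withheld injections (SAP 3.4).** Injections 2 and 3 are conditional. "Subjects who are not treated at the Day 22 and/or Day 43 Visits will complete all other activities", and these subjects are still expected at Day 64 and Day 95. A subject not treated at Day 22 may be treated at Day 43.

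**The concern.** The three lines do not follow one principle. If the aim is equal periods of about 21 days after each injection, sessions 1 and 2 should also close after 21 days when the next injection is not given, and they do not. If the aim is to credit each event to the most recent injection, session 3 should not stop at Day 64. A programmer has to make a decision that the SAP does not state.

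What is at stake is the meaning of the by-session table. It invites the reader to compare related events after the first, second and third injections. Under the present rule a subject with fewer injections can contribute a much longer window to session 1 or 2 than a fully dosed subject does, and late events in fully dosed subjects do not appear.

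There is also a labelling ambiguity. A subject skipped at Day 22 and dosed at Day 43 is receiving a second injection, at a visit that the Schedule of Activities calls Treatment Session 3. The SAP does not say which session that is.

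**Working it through.** The plan gives no figure to reproduce, so the check applies the date rule to every possible start day.

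**Inputs.** Nominal injection days 1, 22 and 43 (SAP 3.3). Day 64 and Day 95 Visits (SAP Table 2). Session limits (SAP 4.8.1.4). Collection through Day 95 for completers (SAP 3.16.1). A session whose next injection never comes is read literally, as open-ended.

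**Start days 1 to 95 falling in each session:**

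| Injections given on | Session 1 | Session 2 | Session 3 | No session | Event starting Day 70 |
|---|---|---|---|---|---|
| Days 1, 22, 43 | 21 | 21 | 21 | 32 | no session |
| Days 1, 22 | 21 | 74 | – | 0 | session 2 |
| Days 1, 43 | 42 | 53 | – | 0 | session 2 |
| Day 1 only | 95 | – | – | 0 | session 1 |

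The session 1 window thus ranges from 21 to 95 days, and session 2 from 21 to 74 days, according to the injections received.

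**Size of the gap for a fully dosed subject.**

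- As elapsed time after first dose: (95 − 64) / (95 − 1) = 31 / 94 = 33%.
- As elapsed time after a Day 43 injection: (95 − 64) / (95 − 43) = 31 / 52 = 60%.
- Counting start days inclusively, as in the table: 32 / 95 = 33.7%.
- The Day 64 and Day 95 Visits each have a window of 5 days either way. The extremes are 90 − 69 + 1 = 22 start days (22 / 90 = 24%) and 100 − 59 + 1 = 42 start days (42 / 100 = 42%).

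**End of follow-up for early terminators.** Collection runs for 28 days after the last dose: 43 + 28 = Day 71 for a Day 43 injection. Last Date in Study (SAP Table 16) is the early termination visit or, for subjects who terminate at a scheduled visit or are lost to follow-up, the latest scheduled visit. A subject dosed on Day 43 who terminates at a Day 64 Visit has a Last Date in Study of Day 64, seven days before collection ends. Last Date in Study is therefore not a safe closing date for a session.

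**Check of the fix.** With a 21-day window after each injection given, every session is 21 days long. The outside-window row holds 95 − 63 = 32 start days after three injections, 95 − 42 = 53 after two, and 95 − 21 = 74 after one. No start day is unassigned.

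**The case against.** The strongest defence is that the Day 64 stop is deliberate. For a fully dosed subject it gives three equal 21-day windows, and running session 3 to Day 95 would give 21, 21 and 53 days. That is a fair reason to prefer fixed windows, and it shapes the fix. It does not rescue the rule, because the windows are equal only when all three injections are given.

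Other limits stand:

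- **Lost events.** A reader might infer that late events disappear from safety reporting. They do not. A related event on Day 70 is still a TEAE and stays in the overall, related, severity and duration tables, in the serious and special-interest tables where it qualifies, and in the listings.
- **Understated risk.** A reader might infer that risk after the last injection is understated. The documents do not show this. The other tables carry the events, and a 21-day window is a legitimate choice if it is labelled and applied evenly.
- **Totals.** A reader might expect session counts to add up to the related-TEAE total. SAP 7.10.2 counts a subject once per class and term, so a subject with the same term after two injections counts in two sessions but once overall. Subject counts need not add up under any rule.
- **Bias between arms.** A reader might infer that withholding in improved subjects distorts the arm comparison. Improvement is one route to withholding (SAP 3.4), but an injection is also not given when the arm cannot be rotated to neutral (Protocol 6.1). No withholding rate is given, and the planned Fisher tests for adverse events are not by session.
- **Undefined, not open.** That sessions 1 and 2 never close is the literal reading. The alternative is that their end is undefined, which is no easier to program.
- **Table shells.** SAP Section 11 places the layouts in Module 2, which is not among the documents reviewed. A footnote there might settle the matter, but the definition belongs in 4.8.1.4.

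**Conclusion.** The concern holds, within one table. SAP 4.8.1.4 is an inconsistent rule: session length depends on the number of injections, and related events from the Day 64 Visit onward have no session in fully dosed subjects. Sessions in that table are therefore not comparable with one another.

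The uncovered period is about a third of the time after first dose at nominal visit days. This must not be read as a third of events, because the documents give no count of late related events. A difference between arms is possible but cannot be estimated from the documents. Overall safety totals are unaffected.

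The day counts rest on nominal visit days and on the open-ended reading of sessions 1 and 2. The Day 64 gap for three-injection subjects does not depend on that reading. This is a minor point, worth correcting because it is cheap.

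**What to change.** In SAP 4.8.1.4:

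1. Define each session by the injection actually given, and state whether a Day 43 injection after a skipped Day 22 counts as session 2 or session 3.
2. Use the same analysis window after every injection, for example 21 days, or until the next injection if that comes earlier.
3. Add a follow-up / outside-window row for all other related TEAEs up to the end of collection under SAP 3.16.1 (Day 95/ET, or 28 days after the last dose for early terminators). Each related event is then assigned exactly once.
4. Use as each session's denominator the subjects who received that injection.

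If full follow-up after the last injection is preferred, end the last session at the end of adverse event collection, not at Last Date in Study, and footnote the unequal window lengths.

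The cost is one short SAP edit and a minor programming change. No data collection changes.

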4.8.2. Vital Signs and Clinical Laboratories

4.8.2.1. Laboratory Values

Clinical laboratory data (hematology and chemistry only) will be analyzed for observed value and change from baseline at Day 95/ET Visit. Refer to Table 16 for definition of baseline.

In addition, subjects reporting any sponsor-defined potentially clinically important (PCI) laboratory values during the study will be analyzed.

PCI laboratory values are presented in Table 13 below.

Parameter	PCI Low: Less than or equal to	PCI High: Greater than or equal to
Hemoglobin (g/L)	100	190
Hematocrit (%)	30	60
Platelets (10 ⁹ /L)	100	650
ALT (U/L)		3×ULN
AST (U/L)		3×ULN
Creatinine (µmol/L)		200
BUN (mmol/L)		14

 Table 13:
 Potentially Clinically Important Laboratory Criteria

ALT=Alanine transaminase; AST=Aspartate transaminase; BUN=Blood urea nitrogen; PCI=Potentially clinically significant; ULN=Upper limit of normal

4.8.2.2. Vital Signs

Vital signs will be analyzed for observed value and change from baseline separately for vital signs on injection days and vital signs at each visit (excluding post injection time points on injection days). Refer to Table 16 for the definition of baseline.

In addition, subjects reporting any sponsor-defined PCI vital sign values during the study will be analyzed.

Vital sign values are PCI if they meet both the observed value criteria and the change from baseline criteria. The PCI vital sign values are presented in Table 14 below.

Parameter	PCI Low	PCI High
Systolic blood pressure	≤90 mm Hg and decrease ≥20 mm Hg from baseline	≥140 mm Hg and increase ≥20 mm Hg from baseline
Diastolic blood pressure	≤60 mm Hg and decrease ≥15 mm Hg from baseline	≥100 mm Hg and increase ≥15 mm Hg from baseline
Pulse rate	≤50 bpm and decrease ≥15 bpm from baseline	\geq 125 bpm and increase \geq 15 bpm from baseline
Respiratory rate ≤ 12 brpm and decrease ≥ 7 brpm from baseline		≥25 brpm and increase ≥7 brpm from baseline
Temperature		≥38.3°C and increase ≥1.1°C from baseline

Table 14:Potentially Clinically Important Vital Sign Criteria

bpm=Beats per minute; brpm=Breaths per minute; PCI=Potentially clinically significant

5. ANALYSIS POPULATIONS

The study will use the following analysis populations for data summaries.

Population	Definition	Displays	
Safety Population	The Safety Population is defined as all randomized subjects who received at least 1 injection of study treatment (EN3835 or placebo).	All demographic, baseline characteristics and safety parameters will be summarized based on this population.	
	Subjects will be included in the Safety Population based on the actual treatment received.		
Intent-to-Treat (ITT) Population	The ITT Population is defined as all randomized subjects who received at least 1 injection of study treatment (EN3835 or placebo). Subjects will be included in the ITT Population based on the planned treatment.		
Modified Intent-to-Treat (mITT) Population	The mITT Population is defined as all ITT subjects who have a valid baseline adapted ASES composite score in the affected shoulder and at least 1 valid adapted ASES composite score after administration of study treatment.	All efficacy analyses will be based on this population.	
	Subjects will be included in the mITT Population based on the planned treatment. Any subjects in the mITT Population are considered evaluable subjects, including early terminated subjects and/or completers.		
Per-Protocol (PP) Population The PP Population is defined as those subjects in the mITT Population who do not have any major protocol deviations which have a significant effect on the primary endpoint.		If more than 10% of the mITT Population is excluded from the PP Population, then select efficacy summaries will be repeated using the PP Population for the sensitivity analysis.	

Table 15:Analysis Populations

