9. STATISTICAL CONSIDERATIONS AND METHODS

9.1. Sample Size Determination

A post hoc analysis was conducted using a subgroup of AUX-CC-871 subjects who were rated with moderate/severe AC based on baseline MRI images. This subgroup displayed a notable treatment effect (EN3835 vs placebo) on the pain and composite components of the adapted ASES questionnaire. This subgroup also displayed a treatment effect trend for the functional component of the adapted ASES. Given this result, the sample size calculation is based on the mean and SD found in this subgroup for the adapted ASES composite score on Day 95. Given a mean change from baseline value of 38.6 for the EN3835 group and 27.6 for the placebo group with an SD of 21.6, a sample size of approximately 142 subjects would be required given a 1:1 randomization and a type I error of 0.05 with a power of 85%. With an expected drop-out rate of approximately 20%, 180 subjects (90 EN3835 and 90 placebo) should be dosed to ensure 142 subjects complete the study.

9.2. **Populations for Analysis**

For the purposes of analysis, the following populations are defined:

- The Safety Population is defined as all randomized subjects who received at least 1 injection of study treatment (EN3835 or placebo). All safety analyses will be based on this population.
- The Intent-to-Treat (ITT) Population is defined as all randomized subjects who received at least 1 injection of study treatment (EN3835 or placebo).
- The Modified Intent-to-Treat (mITT) Population is defined as all ITT subjects who have a valid baseline adapted ASES composite score in the affected shoulder and at least 1 valid adapted ASES composite score after the injection of the study treatment. All efficacy analyses will be based on this population.
- The Per-Protocol (PP) Population is defined as those subjects in the mITT Population who do not have any major protocol deviations. Determination of PP subjects will be completed before the study database is closed and locked. If more than 10% of the mITT Population is excluded from the PP Population, then all efficacy summaries will be repeated using the PP Population for the sensitivity analysis.

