6.3.1. Handling of Missing Data for Sensitivity Analysis of Primary Endpoint

The primary endpoint is the change from baseline in the adapted ASES composite score for the affected shoulder at Day 95. This value could be missing if the subject has missing data due to discontinuation from the study prior to Day 95, due to a missed assessment, lost to follow-up, or other.

A sensitivity analysis using a mixed model with repeat measurements (MMRM) with imputation using a tipping point analysis (refer to section 7.9.4.1) will be performed on the primary endpoint to assess the impact of missing values. If the primary analysis result is not significant (p-value greater than 0.05), no sensitivity analysis (tipping point) will be completed.

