7.9. Efficacy Analyses

Efficacy parameters will be summarized and analyzed by treatment group using the mITT Population.

For primary and secondary analysis, endpoints of the affected shoulder in the EN3835 treatment group will be compared to those in the placebo group.

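### The tipping-point analysis runs in the mITT set, so dosed subjects with no post-dose ASES composite fall outside the analysis meant to test missing Day 95 data

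*SAP*

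**What the plan says.** SAP Table 15 (section 5) admits a subject to mITT only with a valid baseline composite and "at least 1 valid adapted ASES composite score after administration of study treatment". Of that set it says: "All efficacy analyses will be based on this population". Protocol 9.2 has the same rule: "at least 1 valid adapted ASES composite score after the injection of the study treatment. All efficacy analyses will be based on this population".

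SAP 7.9, which contains the sensitivity analysis, opens with: "Efficacy parameters will be summarized and analyzed by treatment group using the mITT Population". Section 7.9.4.1 sets out the tipping-point steps, reuses the 7.9.1 MMRM, and names no population of its own. The ITT set (randomised and dosed) is defined in Table 15, but no display is assigned to it. The per-protocol set is a subset of mITT.

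On purpose, SAP 6.3.1 says the tipping-point analysis "will be performed on the primary endpoint to assess the impact of missing values", and lists the causes of a missing value as "discontinuation from the study prior to Day 95, due to a missed assessment, lost to follow-up, or other". It makes no exception for subjects who leave before giving any post-dose score.

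**The concern.** The set and the purpose do not match. A subject who is dosed and then withdraws consent or is lost before Day 22, with no early termination score, has a missing Day 95 value of exactly the kind SAP 6.3.1 describes. The mITT rule removes that subject before imputation starts.

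This costs the primary MMRM nothing. Its fixed effects are treatment, visit and their interaction, so a subject with no post-baseline value adds no information to it. Delta-adjusted multiple imputation is different: the same subject would be imputed from treatment and baseline, then shifted, and would count in the pooled estimate.

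What is at stake is how the sensitivity result is read. SAP 7.9.4.1 judges robustness by how large a departure from missing at random is needed to lose significance, and notes that no tipping point may be found when little is missing. Removing subjects with no post-dose data lowers the missing share.

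**Working it through.** **Inputs.** From protocol 9.1 and SAP 3.5: mean changes 38.6 and 27.6 (difference 11.0), SD 21.6, type I error 0.05, power 85%, 180 dosed (90 per arm), 142 completing. SAP 6.1 makes efficacy tests two-sided. SAP 7.9.4.1 runs the shift from 0 to the effect observed in the primary analysis.

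**The plan's own figures reproduce.**
- Normal approximation: n per arm = 2 × (1.960 + 1.036)² × 21.6² / 11² = 69.2, so 70 per arm, 140 in total. With the t distribution, 71 per arm (142) gives 85.4% power.
- Dropout: 142 / 0.80 = 177.5, so 178 against the stated 180. In the plan's numbers, 180 − 142 = 38 subjects (21.1%), or 19 per arm, do not complete.

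**Assumptions for the illustration.** The number per arm with no post-dose composite, u, is not in the documents, so a range is shown. All 19 non-completers per arm lack a Day 95 value. Imputation before shifting leaves the observed difference unchanged. The SE is held at the value for 71 completers per arm. The shift is active-only, and u is the same in both arms.

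**Formulas.**
- SE = 21.6 × √(2/71) = 3.625. The smallest significant difference is 1.96 × 3.625 = 7.11 (7.1055 before rounding).
- Imputed share f: 19/90 in all dosed subjects; (19 − u)/(90 − u) in mITT.
- Tipping shift = (observed difference − 7.1055) / f.
- The cap equals the observed difference, so a tipping point is found within the cap only if the observed difference is below 7.1055 / (1 − f).

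| Set | Imputed share | Tipping shift at difference 11 (cap 11) | Tipping shift at difference 8.7 (cap 8.7) | Tips within cap if difference is below |
|---|---|---|---|---|
| All dosed | 19/90 = 21.1% | 18.4 | 7.55 | 9.01 |
| mITT, u = 2 | 17/88 = 19.3% | 20.2 | 8.25 | 8.81 |
| mITT, u = 5 | 14/85 = 16.5% | 23.6 | 9.68 | 8.51 |
| mITT, u = 9 | 10/81 = 12.3% | 31.5 | 12.92 | 8.11 |

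For example, at a difference of 8.7 (z = 8.7/3.625 = 2.40), the margin is 8.7 − 7.1055 = 1.5945. Then 1.5945 / (19/90) = 7.55 and 1.5945 / (14/85) = 9.68.

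**Reading the table.** At the planned difference of 11, every tipping shift lies beyond the cap, so the choice of set changes the margin but not the conclusion. With u = 5, the conclusion differs for observed differences between 8.51 and 9.01. With u = 2, that band is 8.81 to 9.01; with u = 9, it is 8.11 to 9.01. With u = 0, the two sets coincide.

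**The case against.** **The group is probably small.** The adapted ASES is scheduled at Day 22, before injection, and at the early termination visit. Protocol 7.2 asks for early termination procedures when a subject discontinues, and protocol 7.1 encourages subjects who stop treatment to keep attending. That stands, but u need not be zero: protocol 7.2 requires no procedures once consent is withdrawn, and a subject lost to follow-up may give no score.

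**The direction is not fixed.** This also stands. SAP 7.9.4.1 has two further scenarios. With equal shifts and equal missing shares in both arms, the shifts cancel. With a half shift for placebo, the net effect halves. If more placebo than EN3835 subjects leave early, shifting them lowers the placebo mean and can favour EN3835.

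**Stronger readings that the documents do not support.**
- A reader might give each excluded EN3835 subject no improvement at all, a cost of 38.6/90 = 0.43 points each. The SAP caps the shift at the observed effect. At 11, the cost is 11/90 = 0.12 points each.
- A reader might infer that pain after injection drives early loss from the EN3835 arm. The adverse event rates in protocol 2.3 are not split by arm and are not linked to discontinuation.
- A reader might think the exclusions go unreported. SAP 7.1 already summarises the size of each population by treatment group and lists excluded subjects.

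**Conclusion.** The point holds as a mismatch between set and purpose. The set for 7.9.4.1 is inherited from Table 15 and SAP 7.9 rather than stated there, but nothing in the SAP or protocol points to another.

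The size is unknown and probably modest. The omission overstates robustness under the active-only shift with similar exclusions by arm; it is not shown to do so in every scenario. In the illustration it changes what would be reported only over a narrow band of significant results, about half a point wide if 5 per arm are excluded. That rests on the fixed SE and the assumed 19 missing per arm.

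The analysis is also conditional: it runs only if the primary p value is 0.05 or less. It would be wrong to infer that the primary MMRM is compromised.

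**What to change.** In SAP 7.9.4.1 and in the ITT row of Table 15, state that the tipping-point analysis includes all ITT subjects with a valid baseline composite. Every missing post-baseline composite is imputed from treatment, baseline and any observed visits, and then shifted as already specified. Keep mITT for the primary MMRM.

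The PROC MI outline already lists treatment group and baseline among its variables, and a subject with only a baseline value is a monotone pattern, so the method itself need not change.

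Protocol 9.2 also assigns all efficacy analyses to mITT, so the departure should be entered in SAP Table 17.

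The cost is SAP wording and no new data. The downside is a possibly less favourable sensitivity result. If no dosed subject with a baseline composite lacks a post-dose composite, the two sets coincide for this analysis and nothing changes.
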